### 7.5.2. Plasma Sample Shipment to Bioanalytical Laboratory

The shipping procedures and address of the bioanalytical laboratory will be provided under separate cover.

#### 7.6. Blood Volume

Total blood sampling volume for the individual subjects is approximately 36 mL.

### **Blood Volume**

Sample Type	Sample	N	Total Volume		
	Volume (mL)	Screening	Treatment Period	End of Study	(mL)
Safety Labs	6	1		1	12
Pregnancy*	6	1		1	12
PK	6		6 mLX 2		12
TOTAL					36

This total volume does not include discarded blood from pre-draws used to remove fluid from flushed catheters.

### 8. ADVERSE EVENT REPORTING

#### 8.1. Adverse Events

All observed or volunteered AEs regardless of treatment group or suspected causal relationship to the study drug(s) will be reported as described in the following sections.

\* Includes only females of child-bearing age who are sexually active.

For all AEs, the investigator must pursue and obtain information adequate both to determine the outcome of the AE and to assess whether it meets the criteria for classification as an SAE requiring immediate notification to Pfizer or its designated representative. For all AEs, sufficient information should be obtained by the investigator to determine the causality of the AE. The investigator is required to assess causality. Follow-up by the investigator may be required until the event or its sequelae resolve or stabilize at a level acceptable to the investigator, and Pfizer concurs with that assessment.

As part of ongoing safety reviews conducted by the Sponsor, any non-serious adverse event that is determined by the Sponsor to be serious will be reported by the Sponsor as an SAE. To assist in the determination of case seriousness further information may be requested from the investigator to provide clarity and understanding of the event in the context of the clinical trial.

# 8.2. Reporting Period

For SAEs, the active reporting period to Pfizer or its designated representative begins from the time that the subject provides informed consent, which is obtained prior to the subject's participation in the study, ie, prior to undergoing any study-related procedure and/or receiving study drug, through and including 28 calendar days after the last administration of the study drug. Serious adverse events occurring to a subject after the active reporting period has ended should be reported to the Sponsor if the investigator becomes aware of them; at a minimum, all serious adverse events that the investigator believes have at least a reasonable possibility of being related to study drug are to be reported to the Sponsor.

• AEs (serious and non-serious) should be recorded on the CRF from the time the subject has taken at least one dose of study treatment through last subject visit.

#### 8.3. Definition of an Adverse Event

An AE is any untoward medical occurrence in a clinical investigation subject administered a product or medical device; the event need not necessarily have a causal relationship with the treatment or usage. Examples of AEs include but are not limited to:

- Abnormal test findings;
- Clinically significant symptoms and signs;
- Changes in physical examination findings;
- Hypersensitivity;
- Progression/worsening of underlying disease;
- Drug abuse;
- Drug dependency.

Additionally, they may include the signs or symptoms resulting from:

- Drug overdose;
- Drug withdrawal;
- Drug misuse;
- Drug interactions;
- Extravasation:
- Exposure during pregnancy (EDP);
- Exposure via breastfeeding;
- Medication error:
- Occupational exposure.

#### 8.4. Medication Errors

Medication errors may result, in this study, from the administration or consumption of the wrong drug, by the wrong subject, at the wrong time, or at the wrong dosage strength. Such medication errors occurring to a study participant are to be captured on the medication error CRF which is a specific version of the AE page, and on the SAE form when appropriate. In the event of medication dosing error, the sponsor should be notified immediately.

Medication errors are reportable irrespective of the presence of an associated AE/SAE, including:

- Medication errors involving subject exposure to the study drug;
- Potential medication errors or uses outside of what is foreseen in the protocol that do or do not involve the participating subject.

Whether or not the medication error is accompanied by an AE, as determined by the investigator, the medication error is captured on the medication error version of the AE page and, if applicable, any associated AE(s) are captured on an AE CRF page.

# 8.5. Abnormal Test Findings

The criteria for determining whether an abnormal objective test finding should be reported as an AE are as follows:

• Test result is associated with accompanying symptoms, and/or

- Test result requires additional diagnostic testing or medical/surgical intervention, and/or
- Test result leads to a change in study dosing or withdrawal from the study, significant additional concomitant drug treatment, or other therapy, and/or
- Test result is considered to be an AE by the investigator or sponsor.

Merely repeating an abnormal test, in the absence of any of the above conditions, does not constitute an AE. Any abnormal test result that is determined to be an error does not require reporting as an AE.

#### **8.6. Serious Adverse Events**

An SAE is any untoward medical occurrence at any dose that:

- Results in death;
- Is life-threatening (immediate risk of death);
- Requires inpatient hospitalization or prolongation of existing hospitalization;
- Results in persistent or significant disability/incapacity (substantial disruption of the ability to conduct normal life functions);
- Results in congenital anomaly/birth defect.

Medical and scientific judgment is exercised in determining whether an event is an important medical event. An important medical event may not be immediately life-threatening and/or result in death or hospitalization. However, if it is determined that the event may jeopardize the subject or may require intervention to prevent one of the other AE outcomes, the important medical event should be reported as serious.

Examples of such events are intensive treatment in an emergency room or at home for allergic bronchospasm; blood dyscrasias or convulsions that do not result in hospitalization; or development of drug dependency or drug abuse.

### 8.6.1. Potential Cases of Drug-Induced Liver Injury

Abnormal values in aspartate transaminase (AST) and/or alanine transaminase (ALT) levels concurrent with abnormal elevations in total bilirubin that meet the criteria outlined below in the absence of other causes of liver injury are considered potential cases of drug-induced liver injury (potential Hy's Law cases) and should always be considered important medical events.

The threshold of laboratory abnormalities for a potential case of drug-induced liver injury depends on the subject's individual baseline values and underlying conditions. Subjects who present with the following laboratory abnormalities should be evaluated further to definitively determine the etiology of the abnormal laboratory values:

- Subjects with AST or ALT and total bilirubin baseline values within the normal range who subsequently present with AST or ALT ≥3 times the upper limit of normal (X ULN) concurrent with a total bilirubin ≥2 X ULN with no evidence of hemolysis and an alkaline phosphatase ≤2 X ULN or not available.
- For subjects with preexisting ALT **OR** AST **OR** total bilirubin values above the upper limit of normal, the following threshold values should be used in the definition mentioned above:
  - For subjects with pre-existing AST or ALT baseline values above the normal range: AST or ALT ≥2 times the baseline values and ≥3 X ULN, or ≥8 X ULN (whichever is smaller).

#### Concurrent with

• For subjects with pre-existing values of total bilirubin above the normal range: Total bilirubin increased from baseline by an amount of at least 1 X ULN **or** if the value reaches  $\geq$ 3 X ULN (whichever is smaller).

The subject should return to the investigational site and be evaluated as soon as possible, preferably within 48 hours from awareness of the abnormal results. This evaluation should include laboratory tests, detailed history and physical assessment.

In addition to repeating AST and ALT, laboratory tests should include albumin, creatine kinase, total bilirubin, direct and indirect bilirubin, gamma-glutamyl transferase, prothrombin time (PT)/international normalized ratio (INR), and alkaline phosphatase. A detailed history, including relevant information, such as review of ethanol, acetaminophen, recreational drug and supplement consumption, family history, occupational exposure, sexual history, travel history, history of contact with a jaundiced subject, surgery, blood transfusion, history of liver or allergic disease, and work exposure, should be collected. Further testing for acute hepatitis A, B, or C infection and liver imaging (eg, biliary tract) may be warranted. All cases confirmed on repeat testing as meeting the laboratory criteria defined above, with no other cause for liver function test (LFT) abnormalities identified at the time should be considered potential Hy's Law cases irrespective of availability of all the results of the investigations performed to determine etiology of the abnormal LFTs. Such potential Hy's Law cases should be reported as SAEs.

#### 8.7. Hospitalization

Hospitalization is defined as any initial admission (even less than 24 hours) in a hospital or equivalent healthcare facility or any prolongation to an existing admission. Admission also includes transfer within the hospital to an acute/intensive care unit (eg., from the psychiatric

wing to a medical floor, medical floor to a coronary care unit, or neurological floor to a tuberculosis unit). An emergency room visit does not necessarily constitute a hospitalization; however, the event leading to the emergency room visit should be assessed for medical importance.

Hospitalization does not include the following:

- Rehabilitation facilities;
- Hospice facilities;
- Respite care (eg, caregiver relief);
- Skilled nursing facilities;
- Nursing homes;
- Same day surgeries (as outpatient/same day/ambulatory procedures).

Hospitalization or prolongation of hospitalization in the absence of a precipitating, clinical AE is not in itself an SAE. Examples include:

- Admission for treatment of a preexisting condition not associated with the development of a new AE or with a worsening of the preexisting condition (eg, for work-up of persistent pre-treatment lab abnormality);
- Social admission (eg, subject has no place to sleep);
- Administrative admission (eg., for yearly physical exam);
- Protocol-specified admission during a study (eg, for a procedure required by the study protocol);
- Optional admission not associated with a precipitating clinical AE (eg, for elective cosmetic surgery);
- Hospitalization for observation without a medical AE;
- Pre-planned treatments or surgical procedures should be noted in the baseline documentation for the entire protocol and/or for the individual subject.

Diagnostic and therapeutic non-invasive and invasive procedures, such as surgery, should not be reported as AEs. However, the medical condition for which the procedure was performed should be reported if it meets the definition of an AE. For example, an acute appendicitis that begins during the AE reporting period should be reported as the AE, and the resulting appendectomy should be recorded as treatment of the AE.

### 8.8. Severity Assessment

If required on the AE case report forms (CRFs), the investigator will use the adjectives MILD, MODERATE, or SEVERE to describe the maximum intensity of the AE. For purposes of consistency, these intensity grades are defined as follows:

MILD		Does not interfere with subject's usual function.		
	MODERATE	Interferes to some extent with subject's usual function.		
	SEVERE	Interferes significantly with subject's usual function.		

Note the distinction between the severity and the seriousness of an AE. A severe event is not necessarily an SAE. For example, a headache may be severe (interferes significantly with subject's usual function) but would not be classified as serious unless it met one of the criteria for SAEs, listed above.

### 8.9. Causality Assessment

The investigator's assessment of causality must be provided for all AEs (serious and non-serious); the investigator must record the causal relationship in the CRF, as appropriate, and report such an assessment in accordance with the SAE reporting requirements if applicable. An investigator's causality assessment is the determination of whether there exists a reasonable possibility that the study drug caused or contributed to an AE; generally the facts (evidence) or arguments to suggest a causal relationship should be provided. If the investigator does not know whether or not the study drug caused the event, then the event will be handled as "related to study drug" for reporting purposes, as defined by the Sponsor (see the section on Reporting Requirements). If the investigator's causality assessment is "unknown but not related to study drug", this should be clearly documented on study records.

In addition, if the investigator determines an SAE is associated with study procedures, the investigator must record this causal relationship in the source documents and CRF, as appropriate, and report such an assessment in accordance with the SAE reporting requirements, if applicable.

#### 8.10. Exposure During Pregnancy

For investigational products study treatment and for marketed products, an exposure during pregnancy (EDP) occurs if:

1. A female becomes, or is found to be, pregnant either while receiving or being exposed (eg, because of treatment or environmental exposure) to the study drug; or the female becomes, or is found to be pregnant after discontinuing and/or being exposed to the study drug.

An example of environmental exposure would be a case involving direct contact with a Pfizer product in a pregnant woman (eg, a nurse reports that she is pregnant and has been exposed to chemotherapeutic products).

2. A male has been exposed (eg, because of treatment or environmental exposure) to the study drug prior to or around the time of conception and/or is exposed during his partner's pregnancy.

If a study subject or study subject's partner becomes or is found to be pregnant during the study subject's treatment with the study drug, the investigator must submit this information to the Pfizer Drug Safety Unit on a SAE report form and EDP supplemental form, regardless of whether an SAE has occurred. In addition, the investigator must submit information regarding environmental exposure to a Pfizer product in a pregnant woman (eg, a subject reports that she is pregnant and has been exposed to a cytotoxic product by inhalation or spillage) using the EDP supplemental form. This must be done irrespective of whether an AE has occurred and within 24 hours of awareness of the exposure. The information submitted should include the anticipated date of delivery (see below for information related to termination of pregnancy).

Follow-up is conducted to obtain general information on the pregnancy and its outcome for all EDP reports with an unknown outcome. The investigator will follow the pregnancy until completion (or until pregnancy termination) and notify Pfizer of the outcome as a follow up to the initial EDP supplemental form. In the case of a live birth, the structural integrity of the neonate can be assessed at the time of birth. In the event of a termination, the reason(s) for termination should be specified and, if clinically possible, the structural integrity of the terminated fetus should be assessed by gross visual inspection (unless pre-procedure test findings are conclusive for a congenital anomaly and the findings are reported).

If the outcome of the pregnancy meets the criteria for an SAE (ie, ectopic pregnancy, spontaneous abortion, intrauterine fetal demise, neonatal death, or congenital anomaly [in a live born, a terminated fetus, an intrauterine fetal demise, or a neonatal death]), the investigator should follow the procedures for reporting SAEs.

Additional information about pregnancy outcomes that are reported as SAEs follows:

- Spontaneous abortion includes miscarriage and missed abortion;
- Neonatal deaths that occur within 1 month of birth should be reported, without regard to causality, as SAEs. In addition, infant deaths after 1 month should be reported as SAEs when the investigator assesses the infant death as related or possibly related to exposure to study drug.

Additional information regarding the EDP may be requested by the investigator. Further follow-up of birth outcomes will be handled on a case-by-case basis (eg, follow-up on preterm infants to identify developmental delays). In the case of paternal exposure, the investigator will provide the study subject with the Pregnant Partner Release of Information Form to deliver to his partner. The investigator must document in the source documents that the subject was given the Pregnant Partner Release of Information Form to provide to his partner.

### 8.11. Occupational Exposure

An occupational exposure occurs when during the performance of job duties, a person (whether a healthcare professional or otherwise) gets in unplanned direct contact with the product, which may or may not lead to the occurrence of an AE.

An occupational exposure is reported to safety within 24 hours of investigator's awareness, using the SAE Report form, regardless of whether there is an associated AE/SAE. Since the information does not pertain to a subject enrolled in the study, the information is not reported on a CRF, however a copy of the completed SAE Report form is maintained in the study master file.

### 8.12. Withdrawal Due to Adverse Events (See Also Section on Subject Withdrawal)

Withdrawal due to AE should be distinguished from withdrawal due to other causes, according to the definition of AE noted earlier, and recorded on the appropriate AE CRF page.

When a subject withdraws due to an SAE, the SAE must be reported in accordance with the reporting requirements defined below.

# 8.13. Eliciting Adverse Event Information

The investigator is to report all directly observed AEs and all AEs spontaneously reported by the study subject/parent/legal guardian. In addition, each study subject/parent/legal guardian will be questioned about AEs.

#### 8.14. Reporting Requirements

Each AE is to be assessed to determine if it meets the criteria for SAEs. If an SAE occurs, expedited reporting will follow local and international regulations, as appropriate.

### 8.14.1. Serious Adverse Event Reporting Requirements

If an SAE occurs, Pfizer is to be notified within 24 hours of investigator awareness of the event.

In particular, if the SAE is fatal or life-threatening, notification to Pfizer must be made immediately, irrespective of the extent of available AE information. This timeframe also applies to additional new information (follow-up) on previously forwarded SAE reports as well as to the initial and follow-up reporting of exposure during pregnancy and exposure via breastfeeding and occupational exposure cases.

In the rare event that the investigator does not become aware of the occurrence of an SAE immediately (eg, if an outpatient study subject initially seeks treatment elsewhere), the investigator is to report the event within 24 hours after learning of it and document the time of his or her first awareness of the AE.

For all SAEs, the investigator is obligated to pursue and provide information to Pfizer in accordance with the time frames for reporting specified above. In addition, an investigator

may be requested by Pfizer to obtain specific additional follow-up information in an expedited fashion. This information collected for SAEs is more detailed than that captured on the AE CRF. In general, this will include a description of the AE in sufficient detail to allow for a complete medical assessment of the case and independent determination of possible causality. Information on other possible causes of the event, such as concomitant medications, vaccines, and/or illnesses, must be provided. In the case of a subject death, a summary of available autopsy findings must be submitted as soon as possible to Pfizer or its designated representative.

### 8.14.2. Non-serious Adverse Event Reporting Requirements

All AEs will be reported on the AE page(s) of the CRF. It should be noted that the form for collection of SAE information is not the same as the AE CRF. Where the same data are collected, the forms must be completed in a consistent manner. For example, the same AE term should be used on both forms. AEs should be reported using concise medical terminology on the CRFs as well as on the form for collection of SAE information.

# 8.14.3. Sponsor Reporting Requirements to Regulatory Authorities

Adverse event reporting, including suspected unexpected serious adverse reactions, will be carried out in accordance with applicable local regulations.

#### 9. DATA ANALYSIS/STATISTICAL METHODS

Detailed methodology for summary and statistical analyses of the data collected in this study will be documented in a Statistical Analysis Plan (SAP), which will be maintained by the sponsor. This document may modify the plans outlined in the protocol for secondary endpoints; any major modifications of the primary endpoint definition and/or its analysis will be reflected in a protocol amendment.

Additional unplanned analyses may be required after all planned analyses have been completed. Any unplanned analyses will be clearly identified in the final clinical study report.

Descriptive summaries for variables measured on a continuous scale will include the mean, standard deviation, median, minimum, and maximum values. Descriptive summaries for variables measured on a categorical scale will include the number and percentage of subjects who presented each value.

# 9.1. Sample Size Determination

The study plans to enroll approximately 140 subjects for the purpose of establishing a safety database, with at least 100 subjects exposed to at least 2 weeks of the Maintenance Phase with neither age group exceeding a 3:1 margin compared to the other age group (7-11 years old and 12-17 years old).

CC

CCI

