# **Document History**

Document	Version Date	Summary of Changes					
Amendment 2 26 May 2015		A substantial change will be preceded by (SC). All other changes are administrative changes as required by the latest protocol template.					
		Title					
		Removed the word " chronic " from the title and throughout the protocol, to improve recruitment by expanding the subject population to subjects with moderate-to-severe post-surgical pain requiring around-the-clock opioid therapy based on investigators feedback.					
		Protocol Summary					
		Endpoints					
		Primary  • (SC) Pharmacokinetics: volume of distribution (Vd/F) deleted and changed to "average concentration at steady-state (Css, av)," the low fluctuation in plasma concentration-time profile of morphine and the sparse PK Sampling schedule do not support an estimation of Vd/F analysis.  Study Design					
		Added					
	Safety Assessment						
		Pharmacokinetic Assessment					
		Safety Analysis					
		
 
Pharmacokinetic Analysis         (SC) Pharmacokinetics: Vd/F added here data permitting.     
 
					
		Sections 3.3 and 6.3: (SC) Added PK collections to Visit 6/ET, to accommodate PK sample at early withdrawal if not obtained at Visit 4, which was not provided in Amendment 1.					
		Section 4.1 Inclusion Criteria					
		2. (SC) "confirmed moderate-to-severe chronic pain (of cancerous or non-cancerous origin) requiring around-the-clock treatment with an opioid analgesic for an extended period of time." changed to "confirmed moderate-to-severe pain requiring around the-clock treatment with an opioid analgesic, "to remove "chronic and allow for the recruitment of post-surgery subjects."					
		3. (SC) "5 consecutive days" changed to "3 consecutive days" to expand the subject population and to align with the post-surgical days requirement.					

Most post-surgery subjects will be switched to an extended release opioid within 48 to 72 hours if around-the-clock treatment with an opioid analgesic is required.

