		Appendix 6: Becomes C-SSRS Since Last Visit.
Amendment 1 0	05 November 2013	Substantial changes reflect 2 points of advice from FDA (letter dated 08/28/2013) from the Division of Anesthesia, Analgesia, and Addiction Products. They are: 1) a minimum requirement of 100 subjects exposed to a minimum of two weeks of PF-06412528 in the Maintenance Phase and 2) Perform the suicidality assessment (ie, C-SSRS) at every scheduled visit. To comply with FDA, Pfizer has modified the Maintenance Phase to 6 weeks, which includes the FDA 2-week minimum as described in the Statistical Analysis Plan and no more than 6 weeks to facilitate recruitment. A substantial change will be preceded by (SC).  Administrative changes include any grammatical/syntax and minor clarifying changes pertinent to FDA advice. An administrative non-significant change will be preceded by (NSC).  Protocol Summary
		-Study Design
		
 
Completers defined as subjects completing at least
 
2 weeks of maintenance treatment for this 6-week study.
 

		Sample Size Determination
		• (SC) Reference to "100 subjects enrolled" changed to "140 subjects" to account for a 40% discontinuation rate.
		
 
(SC) "An approximately similar number of subjects will be enrolled in each of the two age groups (7-11 years old and 12-17 years old)" changed to "at least 100 subjects completing at least 2 weeks of the Maintenance Phase with neither age group exceeding a 3:1 margin compared to the other age group (7-11 years old and 12-17 years old)."
 
(SC) "N=50 subjects per age group" changed to
 

"100 subjects"

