#### --Safety Analysis

- (NSC) Figure 1 **modified to** accommodate FDA advice on shorter study duration.
- (SC) Reference to "100 subjects enrolled" **changed to** "140 subjects" to account for a 40% discontinuation rate.
- (NSC) Internal Review Committee replaces Data Monitoring Board.

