#### **Study Design:**

This is a multicenter, 6-week, open-label, single-arm study to demonstrate the safety and characterize the PK of PF-06412528 in children 7 to 17 years of age, with moderate-to-severe pain. The study will enroll approximately 140 children to obtain at least 100 subjects exposed to study treatment for at least 2 weeks in the Maintenance Phase. Plasma samples will be collected during the Maintenance Phase at 2 time points under steady-state conditions to characterize the PK of morphine and determine the systemic exposures of naltrexone and 6-β-naltrexol.

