#### **Statistical Method:**

# Sample Size Determination

The study plans to enroll approximately 140 subjects for the purpose of establishing a safety database, with at least 100 subjects exposed to study drug for at least 2 weeks in the Maintenance Phase with neither age group exceeding a 3:1 margin compared to the other age group (7-11 years old and 12-17 years old). Likewise, the study plans to evaluate the PK of morphine in all subjects that provide plasma samples.

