# 1.6. Study Rationale

One of the major challenges facing clinicians who wish to prescribe pain medications to children is the paucity of information in the pediatric population about the proper choice of pain medication, dosage guidelines, and expectations with regard to efficacy and untoward effects. This has led to documented cases of overdosing and under dosing pain medications in pediatric patients. Efforts to address this challenge include the Best Pharmaceuticals for Children Act (BPCA) and the Pediatric Research Equity Act (PREA), which were enacted by Congress "to promote drug development in children because of the inadequacy of pediatric use information for the majority of drug products approved in the United States". 

While the use of morphine to treat pain in pediatric patients with cancer is well recognized, its use to treat other forms of moderate-to-severe pain (eg, arthritis, neuropathic pain) has become apparent only during the past decade. During that same period, new extended-release opioid dosage forms have found their way to the market, but with only limited utility. According to a published Food and Drug Administration (FDA) Workshop on pediatric analgesic trial design, "comparatively few children receive round-the-clock opioids for severe pain for time periods more than 4 weeks." An in-house analysis of Truven (formerly MarketScan) Commercial claims and Encounters database supplied by Truven Health Analytics from October 2011 through September 2012 included an evaluation of 14 million children from 59.4 million Truven enrollees of which 3,000 (0.02%) received an ER opioid prescription. Of those children receiving an ER opioid prescription, 179 (5.8%)

were in the 0-2 years age range, 80 (2.6%) were in the 3-6 years age range, 283 (9.2%) were in the 7-11 years age range, and 2,537 (82.4%) were adolescents in the 12-17 years age range. This study is a post-marketing commitment required by the FDA that will characterize the PK and establish a safety database of PF-06412528 in 100 pediatric pain subjects.

Moreover, the results of this in-house analysis also revealed that very few children (6.1%) treated with opioids take them chronically and even fewer (2.1%) are treated with a long-acting opioid. Therefore, this study will establish a safety database and characterize the pharmacokinetics of PF-06412528 in 100 children with moderate-to-severe pain, as required.

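### The planned 140 equals 100 × 1.40, which does not allow for 40% loss if that loss falls before 2 weeks of Maintenance (167 needed); 140 gives 100 on average only if that loss is at most 28.6%.

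*Protocol*

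**What the plan says.** Three places in the current protocol give the same pair of numbers. Section 9.1 states: "The study plans to enroll approximately 140 subjects for the purpose of establishing a safety database, with at least 100 subjects exposed". The exposure it requires is 2 weeks or more of Maintenance. The Summary, under Study Design, makes the link explicit: "The study will enroll approximately 140 children to obtain at least 100 subjects exposed to study treatment for at least 2 weeks". Those 2 weeks are again counted within Maintenance. Section 3 repeats both figures.

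No visible current section gives a discontinuation rate, and part of 9.1 is blacked out. The reason for 140 appears in the Amendment 1 entries of the Document History, where 100 enrolled became 140 "to account for a 40% discontinuation rate". The same log gives the origin of the target, FDA advice recorded as "a minimum requirement of 100 subjects exposed to a minimum of two weeks of PF-06412528 in the Maintenance Phase". It defines completers by reference to at least "2 weeks of maintenance treatment for this 6-week study". Section 1.6 repeats the number without the 2-week condition: the study is to "establish a safety database of PF-06412528 in 100 pediatric pain subjects".

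SAP 2.1 keeps 140 but sets the target as at least 100 subjects who complete the Maintenance Phase, and describes that phase as lasting 6 weeks.

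**The concern.** An allowance for dropout divides the required number by the share retained. Multiplying by one plus the dropout rate gives too small a figure, and the gap widens as the rate rises. Here 140 is exactly what the multiplication gives at 40%.

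This is not a difference between superseded and current text. Both 140 and 100 are in force, and the log is the one visible explanation of how 140 was reached.

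The 100 is the trial's main visible numerical target, and the log records it as a regulatory minimum. If the recorded rate means loss before a subject reaches 2 weeks of Maintenance, the planned enrolment does not deliver the target. If it means something else, the reader still cannot check 140 against 100, because the visible text gives no loss up to the time point that defines the target.

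**Working it through.** **Inputs.** Required number 100 and planned enrolment 140 (Protocol 9.1). Discontinuation 40% (Amendment 1 log). Treatment Period 7 to 10 weeks, made up of 1 to 4 weeks of Conversion/Titration and 6 weeks of Maintenance (Protocol 3.2, 3.2.1; Schedule of Activities). Amendment 1 design ending at Day 77 to 98, that is 11 to 14 weeks (Document History; SAP 2.1 has the same 4 weeks after treatment).

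**1. Reproduce 140.** 100 × (1 + 0.40) = 140, an exact match.

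**2. Allowance for 40% loss before the qualifying point.** 100/(1 − 0.40) = 166.7, rounded up to 167. This does not reproduce 140.

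**3. Break-even for 140.** 1 − 100/140 = 28.6%.

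**4. Yield of 140 by loss d before 2 weeks of Maintenance.** Expected yield is 140 × (1 − d). The chance of at least 100 is a binomial tail with 140 subjects, independent dropout, and enrolment ending at 140.

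| Loss before 2 weeks | Expected | P(at least 100) |
|---|---|---|
| 20% | 112 | 99% |
| 25% | 105 | 86% |
| 30% | 98 | 40% |
| 35% | 91 | 6% |
| 40% | 84 | 0.3% |

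For an 80% chance of reaching 100, loss must be at most about 26%.

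**5. If the 40% covers a longer span.** Assume a constant rate of loss over T weeks. Loss by week t is d = 1 − 0.6^(t/T), where t is the titration time plus 2 weeks.

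| Span of the 40% | t, T (weeks) | d | Expected | P(at least 100) |
|---|---|---|---|---|
| Treatment Period, shortest | 3, 7 | 19.7% | 112 | 99.6% |
| Treatment Period, longest | 6, 10 | 26.4% | 103 | 75% |
| Amendment 1 design, shortest | 3, 11 | 13.0% | 122 | above 99% |
| Amendment 1 design, longest | 6, 14 | 19.7% | 112 | 99.6% |

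The constant rate matters. For a 40% loss over any span, the expected yield falls below 100 once more than 0.286/0.40 = 71% of it occurs before 2 weeks of Maintenance. Subjects without a stable dose by Visit 3d leave treatment (Protocol 3.2.1), so those losses fall early.

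**6. The SAP 2.1 target (completing 6 weeks of Maintenance).** If all of a 40% loss falls before Maintenance ends, 140 × 0.60 = 84. This is a floor. At a constant rate over 11 to 14 weeks, loss by the end of Maintenance is 1 − 0.6^(7/11) = 28% to 1 − 0.6^(10/14) = 31%, and the expected yield is 101 to 97.

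**The case against.** The strongest reply is that the log gives no time point for the 40%. Read as loss over the whole study, many of those subjects would already have their 2 weeks, and step 5 shows that 140 can then be ample. This stands. Against it, the log's own completer definition is set at 2 weeks of Maintenance, and the current early-termination rule (Protocol 3.2.3) uses the same threshold. These favour the stricter reading without deciding it.

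Three further points stand:

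- Amendment 2 changed the population "to improve recruitment by expanding the subject population to subjects with moderate-to-severe post-surgical pain", and the current text allows the final Maintenance visit to be Visit 4. A rate set under Amendment 1 may no longer apply.
- Section 9.1 continues into blacked-out text, which may hold a fuller rationale. The absence of a visible rate there cannot be counted as an omission. The point rests on the recorded arithmetic.
- The text says approximately 140 and at least 100, and no passage says enrolment stops at 140.

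The SAP difference may also be loose wording. SAP 2.1 still describes the Amendment 1 design, under which completing meant at least 2 weeks.

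**Conclusion.** The point holds in a limited form. The figure 140 does not follow from its recorded basis if the 40% is loss before 2 weeks of Maintenance. On that reading the allowance is 167, and 140 gives 84 on average. On any reading, 140 supports a loss to that point of at most 28.6% on average, or about 26% for an 80% chance of reaching 100. Confidence is high in the arithmetic and medium in any shortfall.

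A reader might infer more than the documents support:

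- **That the trial will almost certainly miss 100.** The 0.3% needs both the strict reading of the 40% and a hard stop at 140. The first is unsettled and the second is stated nowhere.
- **That 167 must be enrolled.** This follows only if 40% is confirmed as the current loss before 2 weeks.
- **That the SAP target gives 84 however the loss is timed.** SAP 2.1 has 4 weeks after Maintenance, and subjects lost there still count as having completed it.

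The SAP mismatch is a separate matter of alignment and adds nothing to the case that 140 was wrongly derived. The study is descriptive, so no hypothesis test, error rate or analysis set is affected.

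**What to change.** In Protocol 9.1, Section 3 and the Summary:

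1. State that 140 enrolled gives at least 100 on average only if loss before 2 weeks of Maintenance is at most 28.6%.
2. Give the loss now assumed up to that time point.
3. Say whether enrolment continues until 100 subjects qualify.

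Do not write 40% or 84 into these sections unless 40% is confirmed as the current assumption. If it is confirmed, restate the expected yield of 140 as 84.

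In SAP 2.1, replace the target of completing the Maintenance Phase with the protocol's: "with at least 100 subjects exposed to study drug for at least 2 weeks in the Maintenance Phase".

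The cost is wording in two documents. Correcting the statement needs no new data and no extra enrolment. The downside is a less favourable stated yield.
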